improved continuation rates (4, 5, 6). We found that remotely teaching a patient how to self-administer a subcutaneous injection is challenging. The provider may be in a home office, and may not have access to the actual medication or the supplies to demonstrate technique. The patient may struggle to understand verbal instruction without a visual demonstration, resulting in ineffective medication administration. Instructional videos currently available online are not specific to adolescents who use self-administered injectable contraception. Peer education can be relatable and effective for adolescent patients (7). We propose that self-administration of subcutaneous injectable contraception may be taught using a peer-to-peer video as a synchronous or asynchronous adjunct to consultation with the healthcare professional. Adolescents may be instructed to watch the video demonstration to help inform them about proper technique and ensure safe administration of their medication while at home. This study aims to validate an existing video as an effective teaching tool by assessing metrics such as clarity of the instructions, rate of error, and satisfaction with the video teaching method to our target population. The video was filmed in accordance with Tufts Medical Center department of Marketing and Communications policies and the adolescent participant in the video was appropriately consented by a parent/guardian. The video was presented as an oral abstract at the North American Society for Pediatric and Adolescent Gynecology Annual Meeting in March 2021.

3. *Describe the relevance and usefulness of the objectives:* The primary objective of this study is to determine the validity of this teaching video for adolescents wishing to learn how to self-administer depot-medroxyprogesterone as an alternative to receiving all injections in a medical office. Having a video option for a teaching tool gives an alternative to in person office visits for teaching and gives more flexibility for patients and providers when in person visits are limited. The secondary outcome is to determine if patients will continue to use the self-administration technique for future injections.

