1. *Describe the potential benefits that individual subjects may experience from taking part in the research. Include the probability, magnitude, and duration of the potential benefits:* If the video is successful and the subject learns how to self-inject, it gives the option of not coming into the doctor's office for every injection which may be more convenient.
Note: Payments and incentives are not considered benefits in the IRB's risk-benefit assessment; payment and incentives should be addressed in the payment section.
2. *Check if there is no direct benefit.*
3. *Describe any benefit to the population from which the subject is drawn:* If this teaching video is deemed to be successful in teaching adolescents to self-administer the subcutaneous depot-medroxyprogesterone, it may be shared on other medical forums and thus benefit a larger audience who then also will have more flexibility and choice about how they receive depot medroxyprogesterone. or N/A
4. *Describe any benefit to science, society, and humanity in general:* Please see answer to #3 above. or N/A

B.4 Alternatives

1. *Describe alternatives to participating in this research study (e.g. to decide not participate in the study, alternative treatments, no treatment (palliative care), etc.):* Alternative is to not participate in the

study and instead receive depot medroxyprogesterone administered by the healthcare provider.

2. *Describe the standard clinical care that may be an alternative:* Receiving the same medication by injection administered by a health care provider. or N/A
3. *Describe how the subject can receive the research procedures/drug/device used in this study in a non-research setting:* or N/A

C. Objectives

1. *Describe the purpose, specific aims, or objectives of the study (i.e. the reason for performing the study in terms of the scientific question to be answered):* Primary aim of this study is to validate that this video, filmed specifically for an adolescent population, is effective at teaching adolescents how to self administer subcutaneous depot medroxyprogesterone. Secondary aims are to determine if the video is deemed satisfactory to the intended viewing audience and to determine if adolescents who watch this video will continue to self administer subcutaneous depot medroxyprogesterone in the future.

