4. *Role of each research team member involved in the informed consent process (Please note, in general, for studies designated by the IRB as greater than minimal risk, a physician PI or Co-I must perform the informed consent process with subjects. A study coordinator/clinical research associate may not consent subjects. A study coordinator/clinical research associate may assist with this process; however, the PI or Co-I should be present to discuss the study with the subject and answer questions, and the PI or Co-I should sign the ICF documenting that s/he has performed the informed consent process with the subject and the subject understands the study.): Consents will be signed with the PI/Co-Is on the research team only.*
5. *Check to confirm you will follow “[SOP: Informed Consent Process for Research \(HRP-090\)](#)”.*

If not, answer all of the following:

- a. *Steps that will be taken to minimize the possibility of coercion or undue influence:*
- b. *Steps that will be taken to ensure subjects' understanding:*
- c. *Describe in detail any other changes that differ from the SOP:*
6. *Check to confirm that Non-English speakers will be enrolled using interpreters and IRB approved Short Forms per the [IRB's Short Form policy](#). If IRB approved Short Forms will not be used, describe which languages the consent will be fully translated into, who will conduct the consent interview, use of interpreters, use of IRB approved translated documents, etc.:*
7. *If non-English speakers are not eligible (excluded from enrollment) for this study, provide the ethical and scientific justification, including whether this would be equitable. For example, if non-English speakers are eligible for the study and could potentially benefit from participation, it would not be equitable to exclude them: Our video at this time is in spoken English with English subtitles only. Providing different languages for the video prior to validation as a teaching tool is not practical. If the video is validated in English, newer versions in different languages may be considered with the assistance of medical interpreters to ensure the verbiage is appropriate.*

Refer to the [IRB Short Form Policy](#) on the IRB website for information about enrolling non-English speakers including how to reach medical interpreters.

8. *Check to confirm you will follow “[SOP: Written Documentation of Consent \(HRP-091\)](#)”.* If not, describe how consent will be documented in writing:

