1. *Describe the primary and secondary study endpoints:* The primary outcome for this study is successful or not successful (i.e., 1/0) self administration of depot-medroxyprogesterone by study participants. A secondary outcome is understanding whether or not study participants will continue to use self administered injections in the future. In addition to these quantifiable outcomes, the study will also collect feasibility information, such as ease of identifying eligible study participants, potential participants willingness to consent, or participants willingness to pick up the prescribed medication prior to an in-person appointment.
2. *Describe any primary or secondary safety endpoints:*

I.2 Sample Size Justification Statistical Analyses

1. *Describe the statistical analyses that will be performed for this study:* This is a pilot study, designed to understand the feasibility of larger scale studies, including those with a comparison group, in the future. Key questions include the statistical properties of the dependent variables, including response rates for survey items and the injection success rate. The analysis will be descriptive, looking at the completeness of the survey data, correlation among survey items, and the injection success rate (to help inform future power analysis, among other things). We will also assess concordance between the observing physician and the patient on the success of the injection using a kappa statistic. Finally, we will compare injection success based a patient's assessment of willingness to continue using self injection in the future. After the initial survey, a

second survey will be given to participants approximately 12 weeks later, to see if participants self inject a second time.

2. *Provide a sample size justification:* Since this is a treatment group-only pilot study, formal power analysis was not conducted. We are targeting 30 participants to better understand how many teenagers complete all steps in the study process (i.e., meet study criteria, consent, pick up medication, attend appointment, attempt injection, complete surveys). The team will make efforts to understand study drop-out at each stage. We also want to better understand the relationship between key covariates, such as convinence of home injection, and the outcome.

I.3 Number of Subjects

1. *Specify the number of subjects to be enrolled in total across all sites:* or N/A this is not a multicenter study.

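### The primary aim is to validate the video as effective, but the design in I.2 is a descriptive single-group feasibility pilot that can only estimate a success proportion

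*Protocol*

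**What the plan says.** **The aim.** Section C states: "Primary aim of this study is to validate that this video, filmed specifically for an adolescent population, is effective at teaching adolescents". B.1 agrees in two places. The background text says "This study aims to validate an existing video as an effective teaching tool", and the item on the relevance of the objectives says "The primary objective of this study is to determine the validity of this teaching video".

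**What may follow.** B.3 item 3 says: "If this teaching video is deemed to be successful in teaching adolescents to self-administer the subcutaneous depot-medroxyprogesterone, it may be shared on other medical forums". G.1 item 7, in justifying the exclusion of non-English speakers, says: "If the video is validated in English, newer versions in different languages may be considered".

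**The endpoint.** I.1 item 1: "The primary outcome for this study is successful or not successful (i.e., 1/0) self administration of depot-medroxyprogesterone by study participants". D.3 item 1 adds that a subject who does not self-administer after the video is recorded as a failure of the video.

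**The design.** I.2 item 1: "This is a pilot study, designed to understand the feasibility of larger scale studies, including those with a comparison group, in the future". The analysis is described as descriptive, and one stated use of the success rate is to inform a later power calculation. I.2 item 2 says there is only a treated group and that no formal power analysis was done. It justifies the target of 30 by interest in how many teenagers complete each study step and in how covariates relate to the outcome. I.3 gives 50 enrolled for 30 completing.

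**Other instruction.** D.4.1 item 1b says subjects receive basic education from the pharmacy when they collect the medication, and so arrive with some instruction on self-injection.

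**The concern.** An aim of validating that something is effective calls for a conclusion: it is, or it has not been shown to be. Sections C and B.1 promise that conclusion, and B.3 and G.1 refer to it as a condition. Section I.2 commits to a study that yields an estimate. Success is defined for each participant, but nothing says what proportion of successes, against what reference or with what confidence bound, would make the video validated. With no such figure fixed in advance, the judgement would have to be made after the data are seen.

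Attribution is a second gap. There is no comparison group, and the video is not the only teaching the subjects receive. A high success rate would describe subjects who had pharmacy instruction and the video together. The exclusion in D.2 of patients who have ever self-injected removes earlier experience but not this instruction.

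At stake is what the study may claim at the end. The primary aim invites a statement that the design does not support.

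**Working it through.** **1. The protocol's own figures.** No alpha, power, target rate or reference rate is given, so there is no power calculation to reproduce. The only arithmetic is 50 enrolled for 30 completing (I.3): 1 − 30/50 = 0.40, and 30/(1 − 0.40) = 50. The 40% is implied by the two numbers and is not stated.

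**2. The sections side by side.**

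| Question | C, B.1, B.3, G.1 | I.2 |
|---|---|---|
| Purpose | Validate the video as effective | Learn whether larger studies are feasible |
| Product | A verdict on which later use may depend | A descriptive success rate, partly to plan a later study |
| Comparison | Effectiveness of the video implied | None; left to future studies |
| Study-level success rate | None given | None given |
| Reason for n | Not given | Completion of study steps; covariate relationships |

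An analysis faithful to the right-hand column does not deliver the aim in the left-hand column.

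**3. The denominator.** Thirty is the number expected to complete the study, surveys included (I.2 item 2, I.3). Success is observed at the first visit (F.2), failure to self-administer counts as a failure, and data collected before withdrawal are kept (D.3). The number analysed for the primary outcome could therefore lie anywhere between 30 and 50, so both ends are shown.

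**4. Precision.** Exact (Clopper-Pearson) 95% limits for x successes in n are: lower = the 0.025 quantile of Beta(x, n − x + 1); upper = the 0.975 quantile of Beta(x + 1, n − x), with upper = 1 when x = n. The observed rates below are assumptions, since the protocol gives none.

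| Observed rate | n = 30 | n = 50 |
|---|---|---|
| 70% | 21/30: 50.6% to 85.3% | 35/50: 55.4% to 82.1% |
| 80% | 24/30: 61.4% to 92.3% | 40/50: 66.3% to 90.0% |
| 90% | 27/30: 73.5% to 97.9% | 45/50: 78.2% to 96.7% |
| 100% | 30/30: 88.4% to 100% | 50/50: 92.9% to 100% |

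For 24/30 the limits come from Beta(24, 7) and Beta(25, 6); for 40/50 from Beta(40, 11) and Beta(41, 10). An observed 80% is compatible with a true failure rate of up to 1 − 0.614 = 38.6% at n = 30, or 1 − 0.663 = 33.7% at n = 50.

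**5. What a pre-stated minimum would demand.** Requiring the lower exact limit to exceed a minimum p0 is an exact binomial test at one-sided alpha of at most 0.025. The minimums and true rates are illustrative assumptions.

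| Minimum p0 | n | Successes needed | Exact alpha | Power if true rate is 90% | Power if true rate is 95% |
|---|---|---|---|---|---|
| 70% | 30 | 27 | 0.009 | 65% | not computed |
| 80% | 30 | 29 | 0.011 | 18% | 55% |
| 70% | 50 | 42 | 0.018 | 94% | not computed |
| 80% | 50 | 46 | 0.019 | 43% | 90% |

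For p0 = 80% at n = 30, power at a true rate of 90% is 0.9^30 + 30 × 0.1 × 0.9^29 = 0.042 + 0.141 = 0.184. A minimum of 90% cannot be exceeded at n = 30, because even 30/30 has a lower limit of 88.4%.

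**The case against.** The strongest reply is that the two descriptions differ mainly in vocabulary. B.1 explains validation as assessing measures such as clarity, error rate and satisfaction, and that is descriptive work of the kind I.2 plans. I.2 is open about the limits: a pilot, descriptive, unpowered, comparison left for later. A single-group pilot needs no hypothesis test, and the choice of interval is commonly left to an analysis plan. Success is defined, per participant. The intervals above show ordinary pilot imprecision, which is not in itself a contradiction.

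Much of this stands. The pilot design is legitimate, the missing criterion is missing only at study level, and the imprecision is expected at this size. What does not stand is the claim that only vocabulary is involved. Section C says that the video is to be validated as effective, which goes beyond describing measures, and B.3 and G.1 use the verdict as a condition. No section says how descriptive results become that verdict. An analysis plan could add an interval, but it could not turn the design in I.2 into a validation.

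Three stronger readings are tempting and are not supported:

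- A reader might infer that a favourable result automatically leads to sharing or translation of the video. Both passages are permissive: the steps may happen or may be considered.
- A reader might infer that the team will report the rate as proof of effectiveness. No passage says so, and I.2 points the other way.
- A reader might infer that the study can achieve none of its purposes. It can estimate the success proportion and describe feasibility.

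**Conclusion.** The point holds as a mismatch between the stated primary aim and the design. The plan supports an estimate of the proportion who self-administer successfully after viewing the video, in subjects who also had pharmacy instruction. It does not support a conclusion that the video has been validated, or that success is due to the video alone.

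The mismatch is visible in the protocol text and rests on no assumption about rates. Its size does depend on assumptions: for an assumed observed rate of 80%, the exact 95% interval spans about 31 percentage points if 30 are analysed (92.3 − 61.4 = 30.9) and about 24 if 50 are (90.0 − 66.3 = 23.7). The remedy lies in the wording of the aim; nothing here argues against running a descriptive pilot.

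**What to change.** Restate the primary aim in C, and the matching statements in B.1, along these lines: *to estimate the proportion of adolescents who successfully self-administer after viewing the video, reported with its exact 95% confidence interval, and to assess the feasibility of a later comparative study.* Naming feasibility matters, because I.2 gives it as the purpose of the pilot and the objectives in C do not mention it. State who is in the denominator. Soften the conditional wording in B.3 item 3 and G.1 item 7 so that it refers to the estimate and no longer to a validated or successful video.

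If a yes/no verdict is wanted, state before enrolment the minimum proportion that the lower limit of the interval must exceed, and check that the number analysed can support it. Even then the conclusion should concern success after the video together with pharmacy instruction.

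The first option changes wording in four sections and nothing in conduct; its downside is a less favourable headline claim. The second may require more subjects or a modest minimum, as the power figures above show.

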G.7 Provisions to Monitor the Study to Ensure the Safety of Subjects	18
G.8 Vulnerable Populations	19
H. Adverse Event Monitoring	23
H.1 Definitions	23
H.2 Reporting Procedures	24
H.3 Reportable New Information	24
I. Statistical Considerations	24
I.1 Study Endpoints	24
I.2 Statistical Analysis	24
I.3 Number of Subjects	25
I.4 Data Management	25
I.5 Randomization	26
J. Drugs or Devices	26
K. Study Administration	27
K.1 Setting	27
K.2 Registration	27
K.3 Resources Available	28
K.4 IRB Review	28
K.5 Multi-Site Research	28
K.6 Community-Based Participatory Research	30
K.7 Sharing Results with Subjects	30
L. References	30

A. Study Schema

Include a diagram that provides a quick “snapshot” of the study. For examples of study schemas, refer to the [FDA and NIH’s Study Schema Examples](#) document available on the IRB website:

1. Prior to enrollment: Determine number of subjects to be enrolled, craft patient and doctor surveys.
2. Enrollment will occur at clinic sites by calling potential subjects in advance to assess interest in the study.
3. If subject expresses interest, doctor or nurse practitioner will call in the subcutaneous form of depot-medroxyprogesterone to pharmacy of patient’s choice, patient will pick up medication prior to scheduled office visit and bring medication with them to the visit.
4. Once patient arrives in clinic with the medication in hand, informed consent / assent will be obtained (consent/assent will be age appropriate and involve parent or guardian if patient is under the age of 18). If subject declines enrollment at this time, doctor will administer the medication.
5. When patient checks into clinic, contact information for patient will be verified including phone number and email address.
6. If consent is obtained, patient will be given video to watch.
7. After video is watched, patient will then self-administer the medication injection while healthcare provider on research team is watching. If there is concern that medication is not being given correctly, doctor/healthcare provider will step in and give the injection to ensure subject gets the correct medication, regardless of the success or failure of the teaching video.
8. After injection is given, subjects will complete a survey in REDCap and study team members will input observational data into REDCap

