Note: Specify which are the primary or secondary aims or objectives of this study as applicable. The primary objective is the main question. Secondary objectives are goals that will provide further information for the study.

D. Enrollment and Withdrawal

D.1 Inclusion Criteria

1. *Describe the criteria that define who will be included in the study as a numbered list:*

Subjects receiving the injection:

1. Assigned females at birth 19 and younger seen at Tufts Medical Center or Tufts Children's Hospital that have previously received at least one injection of depot medroxyprogesterone

Include age eligibility including upper and lower limit.

Indicate specifically whether you will include any of the following special populations: (You may not include members of the populations listed below as subjects in your research unless you indicate them in your inclusion criteria.)

- a. Adults unable to consent (cognitively impaired adults)
- b. Pregnant women
- c. Pregnant minors
- d. Minors, i.e., individuals who are not yet adults (neonates, children, teenagers)
- e. Wards of the state
- f. Non-Viable neonates
- g. Neonates of uncertain viability
- h. Prisoners

If during the course of the study you identify a potential subject who cannot read, write or has some impairment that hampers consent process or documentation, follow the [Policy on Subjects who Cannot Read, Write, or Have Some Impairment that Hampers Consent Process or Documentation](#). If such subjects will be excluded from the study, you must specify that in the "Exclusion Criteria" section below and specify the rationale for their exclusion.

D.2 Exclusion Criteria

1. *Describe the criteria that define who will be excluded in the study as a numbered list:*

Subjects receiving the injection:

1. Any patient who has never received a prior dose of depot medroxyprogesterone.
2. Any patient who has ever self administered any injectable medication (either intramuscular or subcutaneous)
3. Any patient who cannot understand written or spoken English (as the video is currently in English with English subtitles)
4. Any patient under the age of 18 who does not have a parent or guardian to sign the consent form.
5. Subjects who are unable to watch the video due to any circumstances (such as device unavailability or poor wifi signal) will be excluded.

6. Subjects who are cognitively impaired
7. Subjects who are pregnant
8. Wards of the state, prisoners

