2. *Describe in detail how the eligibility criteria will be assessed and satisfied (e.g., medical record review, physical examination):* Study team members will review the clinic schedule ahead of time to find patients who are scheduled for depot-medroxyprogesterone injections and perform chart review to preliminarily determine if patients meet inclusion criteria. These patients will be called via telephone and, using the script provided, will then be asked if they have interest in the study. Inclusion and exclusion criteria will be further clarified with verbal discussion when patients arrive in the office (for example, device availability, wifi signal).
3. *State who will determine eligibility. Note that those who are designated to determine eligibility must have appropriate training, expertise, and oversight, for example a physician PI or Co-I on a biomedical study:* Study team members [name] (PI), [name] and [name] are gynecologists who currently provide care to patients receiving depot medroxyprogesterone and are trained to take care of these patients already. These physicians are also trained to administer both subcutaneous and intramuscular injectable medications. Any study team member added in the future must be a provider trained to care for patients receiving depot medroxyprogesterone injections.
4. *Can study subjects participate in another research study while participating in this research study:*
 Yes No

D.3 Withdrawal of Subjects

1. *Describe anticipated circumstances under which subjects will be withdrawn from the research without their consent:* There is no anticipated circumstance in which subjects would be withdrawn without consent. If the questionnaire is not filled out by the subject, this will be noted, as the provider will still be expected to fill out a separate questionnaire. If the medication is not given by self administration after watching the video, the study data will reflect that outcome as a failure of the video to successfully teach technique.
2. *Describe procedures that will be followed when subjects withdraw or are withdrawn from the research, including the possibility of partial withdrawal from study intervention with continued data collection:* Patients will revert to usual care, which is, receiving depot medroxyprogesterone administered by the healthcare provider. Data collected before the point of withdraw will be retained.

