3. *Describe any necessary safety precautions to be applied to subjects who withdraw or are withdrawn (tapering drug doses, evaluative x-ray, etc.):* or N/A

D.4 Recruitment and Retention

D.4.1 Local Recruitment Methods

Describe the following attributes of the recruitment plan for the local Tufts site:

1. *When, where, and how potential subjects will be recruited:* subjects will be identified in the medical records and screened for eligibility, then receive a telephone call to offer participation prior to scheduled visit
 - a. *If potential subjects will be recruited by telephone, describe how many times the research team will attempt to call / leave a voice message:* 2
 - i. Check to confirm that a script for **both** the telephone conversation and the voice message is included with the submission.
 - b. *When subjects respond to recruitment material, describe the information that will be provided to them about the study and the information that will be collected from subjects (e.g. name, telephone number, etc.). Describe also, how many times you will attempt to respond to*

call the subject back / leave a voice message: Subjects will be offered participation in the study on the telephone. Two attempts to call will be made. If subject expresses interest, their pharmacy details will be collected and a prescription for the subcutaneous version of depot medroxyprogesterone will be sent to their pharmacy. Subject will be instructed to pick up the medication at the pharmacy and bring it to their previously scheduled appointment. Subjects will receive basic education from pharmacy as per SOP, so they will have some prior instruction on how to administer the shot on their own. Subjects will be told on the phone that the doctor will discuss the consent process in person once they are in the office and they are free to proceed or not proceed with the study at that time, but if they decline, the medication will be administered as per standard of care. No additional recruitment calls or materials will be provided or sent.

- i. *Check to confirm that a script for both the telephone conversation and the voice message is included with the submission.*
2. *Source of subjects (for example, patient population, local community, etc.):* Subjects will be drawn from the existing patient population of healthcare providers on the research team

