1. *Summarize the research design and sequentially identify all procedures to be performed to accomplish the specific aims of the project. Clearly identify and distinguish procedures that are considered experimental, procedures that are performed exclusively for research purposes (including "extra" routine tests), and procedures that would occur regardless of the research (i.e., standard of care). Point out any procedures, situations, or materials that may be hazardous, and the precautions to be exercised to maintain subject safety:* 1. Clinic schedules for the medical providers on the research team will be reviewed in advance and any patient that is under the age of 20 and receiving depot-medroxyprogesterone will be contacted by telephone in advance to offer participation in the project. 2. The telephone call will follow the attached script. Two attempts will be made to call patients. 3. If subject is interested in participating, a prescription for the subcutaneous version of depot-medroxyprogesterone will be sent to their pharmacy to be picked up by the subject prior to the office visit. 4. Subjects under 18 will be instructed that they must be accompanied by a parent or guardian. At the office visit, written consent/assent will be obtained. 5. Subject will be shown the instructional video, which is approximately 3 minutes long (video submitted in attached word document with a link, Consent on file for actor in video). They may view as many times as they want. 6. Once ready, the healthcare provider from the research team will observe, without giving verbal instruction, the patient give themselves a subcutaneous depot-medroxyprogesterone injection. 7. If at any point the provider feels that the subject is not performing the injection safely or correctly the healthcare provider will intervene to ensure that the medication is given correctly, and this will be recorded within the REDCap survey. 8. After the injection is given, the subject will fill out the REDCap survey and study team member administering injection will input observational data into REDCap. 9. Subject will be asked to repeat another questionnaire in REDCap at the time of the next injection which will be scheduled for 12 weeks later. The next visit is as per standard of care scheduling (this medication is routinely administered at approximately 12 week intervals). If the subject comes into the same office for the injection, the survey will be filled out in person. If the subject does not come in to the same office, a link to the follow up REDCap survey will be emailed to the subject with instructions on how to access the survey. Email addresses will be confirmed at the time of the first visit, as is routine for medical care.

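### The self-injection result is attributed to the video, but subjects arrive with pharmacy instruction; the aim and the failure rule should name the combined exposure

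*Protocol*

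**What the plan says.** The aim in section C reads: "Primary aim of this study is to validate that this video, filmed specifically for an adolescent population, is effective at teaching adolescents". B.1 likewise speaks of validating an existing video as a teaching tool. D.3, item 1, states that if the drug is not self-administered after viewing, "the study data will reflect that outcome as a failure of the video to successfully teach technique". Step 7 of the study schema has the provider step in when needed, "regardless of the success or failure of the teaching video".

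The recruitment section describes another source of teaching. Under D.4.1, item 1b: "Subjects will receive basic education from pharmacy as per SOP, so they will have some prior instruction on how to administer the shot". The drug is collected before the visit: under schema step 3 the clinician "will call in the subcutaneous form of depot-medroxyprogesterone to pharmacy of patient’s choice".

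Two other sources of learning are controlled. D.2, item 2, excludes anyone who has self-injected any medication before. In F.2, step 6, "the healthcare provider from the research team will observe, without giving verbal instruction".

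I.1 defines the primary outcome as self-administration that is successful or not, scored 1/0. I.2 describes a pilot with a treatment group only and a descriptive analysis, meant to inform larger studies that may include a comparison group.

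**The concern.** The aim and the failure rule assign the outcome to the video, while the recruitment section says that subjects will already have been taught something about giving the injection. The protocol limits learning from earlier self-injection and from the observing provider, which suggests that its authors wanted the result to reflect the video. Pharmacy teaching is the stated exception, and it appears only in a recruitment answer, away from the aim and the outcome.

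What is at stake is the meaning of the reported rate. B.3, item 3, foresees sharing the video more widely if it is judged successful, and G.1, item 7, foresees considering versions in other languages if the English one is validated. Both are tentative, but both rest on a conclusion about the video. The protocol does not say whether those later viewers would have had comparable pharmacy instruction. A rate reported without its condition could be read as applying to people who see only the video.

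**Working it through.** The protocol gives no figure to reproduce here; the question is what the single rate measures.

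**Inputs**

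- Exposure before the visit: basic pharmacy education (D.4.1, item 1b).
- Exposure at the visit: the video, viewed as often as the subject wishes (F.2, step 5), with no verbal coaching (F.2, step 6).
- Outcome: 1/0 self-administration (I.1), with non-self-administration attributed to the video (D.3).
- Groups: one (I.2).

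**Step 1: what is observed.** Write p1 for the probability of success after pharmacy education plus the video, and p0 for the probability after pharmacy education without it. The study estimates p1. No subject is planned to be observed without the video, and no value of p0 is given.

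**Step 2: what the aim would need.** The video's added effect is p1 − p0. Take p1 = 0.90 purely as an assumption:

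| Assumed p0 | p1 − p0 |
|---|---|
| 0 | 0.90 |
| 0.3 | 0.60 |
| 0.5 | 0.40 |
| 0.7 | 0.20 |
| 0.9 | 0 |

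The same observed rate fits every row. The table shows only that the rate does not determine the video's share; it does not estimate the pharmacy contribution. Sample size does not help: whether the denominator is nearer the 30 completers or the 50 enrolled (I.3), more subjects sharpen p1 and say nothing about p0.

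**Step 3: failures.** The same reasoning applies to a score of 0. A subject who does not self-inject has, on the protocol's own account, had both sources of instruction. Scoring 0 is right; describing it as the video's failure assigns a joint result to one component.

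**Step 4: does another section supply the condition?** I.1, I.2 and the data analysis plan in I.4 do not mention pharmacy teaching. B.1 calls the video an adjunct, but to consultation with the healthcare professional, and the aim in C does not repeat that qualifier.

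**The case against.** The strongest reply is that this is an uncontrolled pilot and says so. Even without pharmacy teaching, a single-group rate could not isolate the video's effect. Subjects have all had at least one earlier injection (D.1), and B.1 notes that other instructional videos exist online, so pharmacy education plus video is not the whole of what they bring. Pharmacy education is disclosed, belongs to usual practice, and fits a tool described as an adjunct.

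Much of this stands. The missing comparator is a stated design choice and is not criticised. Using the video on top of usual care is reasonable. The earlier injection is already part of the eligibility definition, so a reader knows of it; the possibility of other instruction is a reason to ask about it in the survey. What the reply does not answer is why the aim and D.3 should credit or blame the video when the protocol itself names a second source of teaching of the same skill.

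A reader might infer more than the protocol supports:

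- That it claims the video works unaided. It never says so; the attribution is implied by the aim and by the wording of D.3.
- That a wrong conclusion has been drawn. None has; I.2 commits only to description.
- That the survey omits pharmacy instruction. F.2, item 1d, says the form is attached, and it is not shown.
- That later power planning is harmed. The combined rate is a suitable input for the video arm if both arms of a later study receive pharmacy education.

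**Conclusion.** The point holds as a matter of attribution. As designed, the primary outcome gives the rate of self-injection after usual pharmacy education plus the video, while C and D.3 describe it as a result of the video. This rests on taking D.4.1 at its word that subjects will have had some instruction; the protocol does not say what it covers or whether it is the same across pharmacies.

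The size of the misattribution cannot be derived from the protocol, and none is claimed. Sample size, outcome coding and conduct are unaffected. A reader might be tempted to conclude that the study cannot meet any useful aim; that goes too far, since the combined rate, survey completeness and feasibility remain informative for a pilot. Priority is minor: a cheap improvement that makes the aim match what I.2 can deliver.

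**What to change.** 1. **Wording.** In C, add to the aim the phrase *after usual pharmacy education plus the video*. In D.3, keep the score of 0 but describe it as *not successful after usual pharmacy education plus the video*. Align schema step 7 and B.1 in the same sense; what the provider does at step 7 is not touched. Add one sentence to I.2: conclusions apply to the combined exposure, and video-specific effectiveness is left to a later comparison-group study. The definition of success in I.1 need not change for this purpose.
2. **Record the exposure.** If the REDCap form does not already do so, add one or two items, answered after consent and before the video: whether instruction on self-injection was received from the pharmacy or elsewhere, and in what form. Report the answers as frequencies only. The subject survey currently follows the injection (schema step 8), so these items would need a short entry ahead of it.

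The cost is a few sentences in A, B.1, C, D.3 and I.2, and about a minute of survey time per subject. The downside is a more modest claim than validation of the video.
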